#### **4.1.6.2 Presentation**

Disease characteristics will be summarised by treatment group and in total for the FAS.

### **4.1.7 Medical History and Concomitant Disease**

#### **4.1.7.1 Definitions and Derivations**

Medical history will be coded using the Medical Dictionary for Regulatory Activities (MedDRA) [Version 24.1 (or a later version if updated during the study)].

#### **4.1.7.2 Presentation**

The number and percentage of participants with any medical history will be summarised for the SSO and by treatment group and in total for the SSR. The number and percentage of participants with at least one medical history record within each primary SOC and PT will be presented. The summary will be sorted alphabetically by SOC and PT. A participant can have one or more PTs reported under a given SOC but will be reported once per PT and SOC.

### **4.1.8 Prior and Concomitant Medications**

#### **4.1.8.1 Definitions and Derivations**

Medications received prior to or concomitantly with study treatment will be coded using the WHO Drug Dictionary [Version March 2021 (or a later version if updated during the study)], Anatomical Therapeutic Chemical (ATC) Classification codes.

Prior medications and concomitant medications are defined as follows:

Prior medications are those taken with a stop date prior to the first dose date of study treatment during the inpatient period.

Concomitant medications during the inpatient period are those with a stop date prior to the first dose of study treatment during the outpatient period and either a start date on or after the first dose date of study treatment during the inpatient period, or those with a start date before, and either a stop date on or after the first dose date of study treatment during the inpatient period or those which are ongoing.

Concomitant medications during the outpatient period are those with a start date on or after the first dose date of study treatment during the outpatient period, or those with a start date before, and either a stop date on or after the first dose date of study treatment during the outpatient period or those which are ongoing.

If a medication cannot be classified as “prior” or “concomitant during the inpatient period” or “concomitant during the outpatient period” after applying imputation rules for missing/incomplete dates, it will be classified as concomitant during the outpatient period.

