- ^k Treatment with sodium zirconium cyclosilicate (SZC) will be established while the participant is in the hospital. Only participants randomised to SZC will be dispensed study intervention during the outpatient phase. Any time study drug dose is adjusted, or if in either treatment arm a concomitant medication which may affect K⁺ levels is changed (eg, use of renin angiotensin-aldosterone system inhibitors [angiotensin-converting enzyme inhibitors, angiotensin receptor blocker, mineralocorticoid receptor antagonists] or diuretics), the participant needs to return to the site 7 (± 2) days later for a K⁺ measurement and recording of adverse events and concomitant medications. During the inpatient phase, drug dispensation will occur every day.
- ^l Central laboratory K⁺ results at baseline are not necessary to initiate the study intervention as long as all eligibility criteria are met (only local assessment of K⁺ within 24 hours of treatment initiation is required).
- ^m If dose titration occurs at any time during the outpatient phase, unscheduled dispensation visits will be performed.
- ⁿ Relative to the date of randomisation (Visit 3)
- ^o Relative to the date of Visit 10/EOT.

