^a Any time study drug dose is adjusted, or if in either treatment arm, a concomitant medication which may affect K⁺ levels is changed (eg, use of RAASi or diuretics), the participant needs to return to the site 7 (\pm 2) days later for a K⁺ measurement and recording of adverse events and concomitant medications.

Participants randomised to Arm B will be discharged without SZC and will receive SoC per local practice for managing their K⁺ until the EOT (180 days post-discharge). The SoC will be at the discretion of the treating physician; however, participants intended to be discharged with a K-binder will not be randomised. However, participants in Arm B may have a K-binder prescribed at Day 7 post-discharge (or after Day 7 post-discharge) to treat confirmed HK or in case there is an increase in K⁺ level since discharge that, in the investigator's opinion, requires therapy.

The K⁺ levels will be measured at on-site visits at Days 7 (local laboratory), 90 (local and central laboratories), and 180 (local and central laboratories) (see Sections 8.1.1 and 8.2.4). Overall monitoring frequency will depend upon a variety of factors including other medications, progression of CKD, and dietary K⁺ intake. It is the responsibility of the treating physicians to check the participant K⁺ as medically appropriate/in accordance with the label (for both SZC and SoC arms). In addition to the scheduled on-site visits, participants should return to the site for a local K⁺ measurement 7 (\pm 2) days after any dose adjustment to SZC.

Additionally, participants in either treatment arm should have their K⁺ measured locally 7 (\pm 2) days after changes are made to medications that affect K⁺ levels (eg, use of RAASI or diuretics).

Such additional K⁺ checks and site visits will take place as clinically indicated and the resulting data, including AEs and concomitant medication information, relating to these visits will also be collected during the study.

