6.6 Study Intervention Compliance

When participants are dosed at the site, which will occur during the inpatient phase, they will receive SZC directly from the investigator or designee, under medical supervision. The date, and time if applicable, of dose administered in the hospital will be recorded in the source documents and recorded in the eCRF. The dose of SZC and study participant identification will be confirmed at the time of dosing by a member of the study site staff other than the person administering the study intervention.

When participants self-administer study interventions at home (SZC or SoC), compliance with study interventions will be assessed at each visit (both on-site and telephone visits).

Compliance will be assessed by counting returned sachets and direct questioning during the visits and documented in the source documents and eCRF. Deviation(s) from the prescribed dosage regimen should be recorded in the eCRF and in the source documentation.

A record of the number of SZC sachets for SZC dispensed to and taken by each participant must be maintained and reconciled with study intervention and compliance records. Intervention start and stop dates, including dates for intervention delays and/or dose reductions or increases will also be recorded in the eCRF.

There will not be accountability for participants allocated to SoC.

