### **3.3.1.1 Screening / Baseline Period**

For all subjects, the screening period is defined as the period from informed consent to the first dose of SZC. For some variables, data from more than one assessment within the screening period may be collected prior to the first dose of SZC.

The baseline value for a variable is therefore defined as the last non-missing observation before the first dose of study treatment (SZC) in the inpatient period. For assessments on the day of first dose, where time is not captured, a nominal pre-dose indicator, if available, will serve as sufficient evidence that the assessment occurred prior to first dose. Any observation made after the first dose of study treatment will be considered post-baseline.

Assessments on the day of the first dose when neither time nor a nominal pre-dose indicator are captured will be considered prior to the first dose if such procedures are required by the protocol to be conducted before first dose.

In all quantitative summaries from baseline, absolute changes from baseline will be calculated as the post-baseline value minus the value at baseline. The percentage change from baseline will be calculated as  $[(\text{post-baseline value} - \text{baseline value}) / \text{baseline value}] \times 100$ .

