#### **4.1.8.2 Presentation**

Prior medications, concomitant medications during the inpatient period and concomitant medications during the outpatient period will be listed separately. Prior medications will be summarised overall using the SSO. Concomitant medications during the inpatient period will be summarised overall using the SSO. Concomitant medications during the outpatient period will be summarised by treatment group and overall using the SSR.

The number and percentages of participants using each medication will be displayed together with the number and percentage of participants using at least one medication within each therapeutic class (ATC-Level 2), chemical subgroup (ATC-Level 4), and generic term. The summaries will be sorted using numerical counts by descending order of therapeutic class, then descending order of chemical subgroup, then descending order of generic term in the total column. Where groups or terms tie these will be sorted alphabetically.

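### The SAP divides inpatient from outpatient concomitant medication at the first outpatient SZC dose, a date that Arm B does not have at discharge

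*SAP*

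**What the plan says.** SAP 4.1.8.1 defines three classes of medication. Prior medications stop before the first inpatient dose. For the next class, "Concomitant medications during the inpatient period are those with a stop date prior to the first dose of study treatment during the outpatient period", followed by alternative conditions on the start date. The outpatient class opens with "those with a start date on or after the first dose date of study treatment during the outpatient period" and adds drugs that began earlier and either stopped on or after that date or are ongoing. For a medication that fits none of these once date imputation has been applied, "it will be classified as concomitant during the outpatient period".

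The two concomitant classes feed different tables in SAP 4.1.8.2. The inpatient class is summarised overall on the Safety Set Open (SSO). For the other, "Concomitant medications during the outpatient period will be summarised by treatment group and overall using the SSR".

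The SAP identifies study treatment with SZC: in 3.3.1.1 the baseline value is the last one "before the first dose of study treatment (SZC) in the inpatient period". After discharge only one arm receives it. Protocol 6.2 says: "Participants randomised to Arm B will be discharged without SZC and will receive SoC per local practice". A footnote to the Schedule of Activities says: "Only participants randomised to SZC will be dispensed study intervention during the outpatient phase". Protocol 6.6 adds: "There will not be accountability for participants allocated to SoC".

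**The concern.** The boundary between the two classes depends on an event that occurs at discharge in one arm only. The Safety Set Randomised (SSR) admits Arm A participants only if they took SZC after randomisation, but admits all of Arm B (SAP 3.2). Every Arm A participant in the by-arm table therefore has the boundary date, and no Arm B participant has it at discharge. An identical in-hospital prescription can be classed differently by arm.

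At stake is the table that shows readers which medications each arm took after discharge. In an open-label comparison with local-practice standard of care (SoC), that table describes the comparator. If acute in-hospital treatment appears there for Arm B alone, or ongoing home medication is missing for Arm B alone, the description is wrong. The SSO inpatient table is also affected, because participants who received SZC in hospital but were never randomised have no outpatient dose either.

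**Working it through.** The plan gives no figure on this point, so the check is to apply the rule to specimen records.

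**Inputs.** The class definitions and default come from SAP 4.1.8.1, the meaning of study treatment from SAP 3.3.1.1, and the absence of outpatient SZC dispensing in Arm B from Protocol 1.3 and 6.2. The timeline is an assumption for illustration: first inpatient SZC dose on day 1, randomisation and discharge on day 8, first outpatient dose on day 8 in Arm A and none in Arm B. A comparison with a date that does not exist counts as not met.

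**Two readings.** The and/or wording of the inpatient definition can be bracketed in two ways.

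- Reading 1: (stop before the outpatient dose AND start on or after the inpatient dose) OR (start before the inpatient dose AND (stop on or after it OR ongoing)).
- Reading 2: stop before the outpatient dose AND (either of the start conditions).

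**Results.**

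| Start and stop day | Reading | Arm A | Arm B as written | Arm B, boundary at randomisation |
|---|---|---|---|---|
| -5 to -1 | both | prior | prior | prior |
| 2 to 4 | both | inpatient | outpatient by default | inpatient |
| -5 to 4 | 1 | inpatient | inpatient | inpatient |
| -5 to 4 | 2 | inpatient | outpatient by default | inpatient |
| 2 to 20 | both | outpatient | outpatient by default | outpatient |
| -5, ongoing | 1 | inpatient and outpatient | inpatient only | inpatient and outpatient |
| -5, ongoing | 2 | outpatient | outpatient by default | outpatient |
| 30 to 40 | both | outpatient | outpatient by default | outpatient |

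Three things follow.

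1. A drug both started and stopped between the first inpatient SZC dose and discharge (day 2 to 4) is classed differently by arm under either reading.
2. For drugs started before the first inpatient dose the answer depends on the reading. Under reading 1 an ongoing home drug is missing from Arm B's outpatient table; under reading 2 a drug stopped in hospital is wrongly added to it.
3. Even a genuine post-discharge drug (day 30 to 40) reaches the outpatient class in Arm B only through the default. With randomisation as the boundary, all six histories agree between arms and the default is never used.

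**Participants without the date.** The protocol plans 163 enrolled and about 130 randomised 1:1, so 130 / 2 = 65 in Arm B, all without the date at discharge. A further 163 - 130 = 33 are not randomised. Those of the 33 who received SZC belong to the SSO. Their in-hospital drugs that fall to the default go to a class tabulated only on the SSR, to which they do not belong, so those records appear in neither concomitant-medication table.

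**The boundary used elsewhere.** Outpatient Day 1 (SAP 3.3.1), the start of the outpatient period (3.3.1.2), outpatient treatment-emergent adverse events (4.6.2.1) and RAASi use at discharge (4.2.25.2) are all tied to the date of randomisation. SAP 3.3.1.2 also ends the inpatient period of non-randomised participants at 21 days after the first SZC dose.

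**The case against.** The default mentions imputation of missing or incomplete dates, so it was probably written for unresolved records. Protocol 4.2 and 6.6 also treat SoC as a study intervention, and Arm B may later receive SZC as a rescue binder. A programmer who follows the rest of the SAP would probably use randomisation anyway.

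The likely intent of the default stands, but as written it covers any medication that cannot be classified. If it is confined to missing dates, Arm B's drugs given wholly in hospital have no class at all, so the rule still needs repair. No first SoC dose date is defined anywhere. A rescue SZC date falls after discharge and would put the boundary in the wrong place. Using randomisation without saying so would be an undocumented departure from the SAP.

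A reader might infer more than the documents support:

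- *All in-hospital drugs in Arm B are misplaced.* This is certain only for those started on or after the first inpatient SZC dose and stopped before discharge. Treatment completed before that dose is prior in both arms.
- *The table is biased in favour of SZC.* Acute treatments can be overcounted in Arm B, but under reading 1 its ongoing home drugs are undercounted.
- *Every Arm B participant, or (65 + 33) / 163 = 60% of those enrolled, is misclassified.* These figures count people without the date, not wrong records. The non-randomised are outside the SSR, and because enrolled means consented, some may never have taken SZC.
- *In-hospital binders will appear as post-discharge SoC.* Protocol 4.1 has any current binder other than SZC stopped at baseline, so a binder continued until discharge is not the planned pathway.

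**Conclusion.** The point holds as a defect in a stated rule: the same in-hospital record can be classed differently according to arm. It rests on reading study treatment as SZC, which the SAP itself does, and on applying the default as worded. All 65 planned Arm B participants lack the boundary date at discharge. The number of misclassified records cannot be derived, because the documents do not say how often qualifying in-hospital drugs are given, and the net direction is not fixed.

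The effect is limited to descriptive medication tables and listings. A reader might suppose that the rescue-therapy or RAASi endpoints are touched. They are not: both kinds of event are determined by the blinded adjudication committee (Protocol Appendix A 5; SAP 4.2 for rescue therapy), and RAASi use at discharge is tied to randomisation. No tested endpoint changes. The correction should be made because it is cheap and the affected table describes the comparator.

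**What to change.** In SAP 4.1.8.1:

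1. Replace the first outpatient dose by the date of randomisation in both concomitant definitions, for both arms.
2. For non-randomised participants, use the end of the inpatient period already defined in SAP 3.3.1.2.
3. Bracket the and/or conditions so that only one reading is possible.
4. Restrict the outpatient default to randomised participants whose medication dates remain unresolved after imputation, and state where unresolved records of non-randomised participants go, since they have no outpatient period.

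The cost is a short text change and a matching change to the program. No new data are needed.

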#### **4.1.8.2 Presentation**

Prior medications, concomitant medications during the inpatient period and concomitant medications during the outpatient period will be listed separately. Prior medications will be summarised overall using the SSO. Concomitant medications during the inpatient period will be summarised overall using the SSO. Concomitant medications during the outpatient period will be summarised by treatment group and overall using the SSR.

The number and percentages of participants using each medication will be displayed together with the number and percentage of participants using at least one medication within each therapeutic class (ATC-Level 2), chemical subgroup (ATC-Level 4), and generic term. The summaries will be sorted using numerical counts by descending order of therapeutic class, then descending order of chemical subgroup, then descending order of generic term in the total column. Where groups or terms tie these will be sorted alphabetically.

#### **4.1.9 Study Intervention Compliance**

##### **4.1.9.1 Definitions and Derivations**

The percentage compliance for SZC will be calculated overall in the inpatient period and in arm A in the outpatient period only and is calculated as:

$$\text{Compliance (\%)} = \frac{(\text{Number of sachets dispensed in inpatient/outpatient period} - \text{Number of sachets returned in inpatient/outpatient period})}{\text{Number of days on treatment in inpatient/outpatient period} \times \text{Number of sachets prescribed per day}}$$

Number of days on treatment will be calculated as follows:

(last dose of SZC in inpatient/outpatient period – first dose of SZC in inpatient/outpatient period)+1.

The percentage compliance for SZC will be calculated separately for the inpatient and outpatient periods and will be summarised descriptively overall using the SSO and in Arm A using the SSR respectively.

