6.1 Screening and Inpatient Phase

Participants with HK (see inclusion criterion #4) and not on SZC or patiromer before this current ED visit/hospital admission (initiation of SZC or patiromer during ED visit/hospitalisation preceding enrolment is allowed), will start SZC, as per local label, during the inpatient phase. Initiation of SZC treatment will be based on local measurement of K⁺, obtained within 24 hours prior to first dose of on-study SZC:

- Correction treatment: 10 g, TID for up to 72 hours. Typically, NK is achieved within 24 to 48 hours. If participants are still hyperkalaemic after 48 hours of treatment, the same regimen can be continued for an additional 24 hours. If NK is not achieved after 72 hours of treatment, other treatment approaches should be considered, and the participant discontinued from the study due to lack of SZC effect. Participants who received any HK treatment during current ED visit/hospitalisation preceding enrolment and are NK at baseline can directly start the maintenance dose of SZC (see hereafter).
- Maintenance treatment (once NK [K^+ between 3.5 and 5.0 mmol/L, inclusive] is reached): 5 g, QD. Dose will be adjusted based on K^+ (see [Table 4](#)). The recommended maintenance dose range is from 5 g every other day to 10 g daily.

Participants with NK and who have been started on a maintenance dose for SZC (per local label) at the time of discharge will be randomised at discharge to either Arm A (SZC per local label) or Arm B (SoC, as per local practice) and enter the outpatient phase.

The following participants will not be eligible for randomisation:

- Participant intended to be discharged on a K-binder as per the site routine medical practice (discontinued from the study)
- Participant with an in-hospital phase exceeding 21 days (including screening), except when study medical monitor's approval was sought for longer duration of hospital stays for specific participants
- Participants with $K^+ > 5.0$ mmol/L at discharge; these participants will be discontinued from the study treatment and followed up as per protocol
- Participants with $K^+ < 3.5$ mmol/L at discharge; these participants will be discontinued from study treatment and will be followed per protocol.

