6.2 Outpatient Phase

Participants randomised to Arm A will be discharged with SZC dosed per local label (from 5 g every other day to 10 g daily) to manage K^+ until the EOT (180 days post-discharge).

As per label, SZC dose titration will be allowed based on K^+ levels as detailed in [Table 4](#).

Table 4 Dose Titration and Discontinuation Criteria During the Outpatient Phase

K^+ (mmol/L)	Dose Titration and Discontinuation Criteria for Abnormal K^+
< 3.0	
• Treatment permanently discontinued (see Section 7.1.1). Check ECG and treat according to medical judgment.
3.0 - 3.4	
• Check ECG, permanently discontinue treatment if serious arrhythmia found and treat according to medical judgment.

K⁺ (mmol/L)	Dose Titration and Discontinuation Criteria for Abnormal K⁺
	
 • If no serious arrhythmia found, investigator to consider to down-titrate^a or pause SZC and treat according to medical judgment. Participants with heart failure should pause study drug. • Increase monitoring until K⁺ \geq 3.5 mmol/L.^a • Evaluate for underlying risk for hypokalaemia. If hypokalaemia resolves and participant deemed appropriate to restart treatment (for participants who have paused SZC), then the investigator should consider to restart SZC at a lower dose.^a
3.5 - 5.0	
 • No change in SZC dose is recommended.
5.1 – 5.5	
 • Increase SZC dose by 5 g QD increments up to a maximum of 10 g QD.^a • Increase monitoring until K⁺ in normal range.
5.6 – 6.0	
 • Check ECG, discontinue treatment if serious arrhythmia found and treat according to medical judgment. • If no serious arrhythmia, increase SZC dose by 5 g QD increments up to a maximum of 10 g QD.^a • Further K⁺ monitoring and treatment per investigator medical judgment based on participant risk and benefit. • Increase monitoring frequency until K⁺ in normal range.
> 6.0	
 • Treatment permanently discontinued (see Section 7.1.1); initiate rescue therapy (see Section 6.7.1 for rescue therapy). • Check ECG and treat according to medical judgment.

Abbreviations: ECG = electrocardiogram; K⁺ = potassium; QD = once daily; RAASi = renin angiotensin-aldosterone system inhibitor; SZC = sodium zirconium cyclosilicate.

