7.1.2 Temporary Discontinuation

If K^+ ranges from 3.0 to 3.4 mmol/L, the investigator will consider SZC administration to be either down-titrated or paused and hypokalaemia should be managed as per standard practice. Participants with heart failure should pause study drug. The participant should be evaluated for any risk factors for hypokalaemia, including any intercurrent illness or comorbidity. Sodium zirconium cyclosilicate administration can be resumed (if paused), if indicated, but only after the intercurrent medical condition that precipitated the hypokalaemia has improved and K^+ has returned to the target range of normal levels (3.5 to 5.0 mmol/L, inclusive). The investigator will consider re-starting SZC with a lower dose.

If participant temporarily (≤ 14 days) discontinues study intervention for reasons other than hypokalaemia, SZC administration can be resumed once participant condition is stabilised according to investigator judgement, and if the participant is willing to take treatment.

Any time study drug dose is adjusted, or if a concomitant medication which may affect K^+ levels is changed (eg, use of RAASi or diuretics), the participant needs to return to the site 7 (± 2) days later for a K^+ measurement and recording of AEs and concomitant medications.

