#### 4.1.9.2 Presentation

Compliance will be summarised separately for the inpatient and outpatient periods using the SSO and SSR respectively using descriptive statistics (n; Mean; SD; Minimum; 1st quartile; Median; 3rd quartile, Maximum) with the number and proportion of participants in the following compliance categories:

- <50%
- $\geq 50\%$  to <80%
- $\geq 80\%$  to <120%
- $\geq 120\%$

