## **4.6.1      Exposure**

### **4.6.1.1    Definitions and Derivations**

Exposure (i.e. duration of treatment) will be defined as follows:

Total (or intended) exposure of study treatment

- Total (or intended) exposure = min (last dose date where dose > 0g, date of death, date of discontinuation) – first dose date + 1

The dosage (g/day) will be calculated for the inpatient period and outpatient period respectively:

The total cumulative dose received (g)/Number of days receiving study drug (i.e. excluding dose interruptions)

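### The SZC compliance formula has one prescribed-rate term over calendar days and no rule for dose changes or instructed pauses, so full adherence need not score 100%

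*SAP*

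**What the plan says.** SAP 4.1.9.1 defines percentage compliance, separately for the inpatient and outpatient periods. The numerator is sachets dispensed minus sachets returned. The denominator is days on treatment times "Number of sachets prescribed per day". Days on treatment is a calendar span: "last dose of SZC in inpatient/outpatient period – first dose of SZC in inpatient/outpatient period)+1". No sentence says which rate applies once the dose has changed, and none removes days on which treatment was paused.

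SAP 4.1.9.2 then summarises the percentage "with the number and proportion of participants in the following compliance categories": <50%, 50 to <80%, 80 to <120%, and 120% or more.

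The protocol varies the prescribed rate by design:

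- In hospital (Protocol 6.1): "Correction treatment: 10 g, TID for up to 72 hours", followed by maintenance that starts at 5 g once daily.
- After discharge (Protocol 6.2): a range "from 5 g every other day to 10 g daily", titrated by Table 4.
- Pauses (Protocol 7.1.2): at potassium of 3.0 to 3.4 mmol/L the investigator considers down-titration or a pause, and "Participants with heart failure should pause study drug". Interruptions for other reasons may last up to 14 days. No maximum is given for a hypokalaemia pause.

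For average dosage, SAP 4.6.1.1 takes the other approach to pauses and divides by "Number of days receiving study drug (i.e. excluding dose interruptions").

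**The concern.** A compliance measure should return about 100% for someone who took exactly what was prescribed. A product of one rate and one calendar span does so only if the rate never changes and treatment is never paused. Anyone randomised after correction treatment has had at least two inpatient rates, because randomisation requires that maintenance has started. Outpatient titration and pauses add further departures.

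At stake is whether the compliance tables can be read at all. Readers use them to judge how fully a titrated drug was taken, and Protocol Table 2 reports oedema-related events that rise with SZC dose. A spread across the bands could then reflect titration rather than adherence, and two programmers could produce different tables from the same data without either departing from the SAP.

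**Working it through.** The plan states no compliance figure, so there is none to reproduce. The check applies the SAP formula to participants who take every prescribed sachet, where the right answer is 100%.

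**Inputs.** Sachets are 5 g (Protocol Table 5). So 10 g three times daily is 6 sachets a day, 10 g daily is 2, 5 g daily is 1, and 5 g every other day averages 0.5. Correction lasts up to 72 hours, taken as 1 to 3 whole days. Inpatient treatment lasts 1 to 21 days (Protocol 4.1) and the outpatient phase 180 days. Days of dose change and lengths of pause are illustrative. Where the rate changes, the starting rate and then the last rate serve as the single rate.

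**Formula.** Compliance = 100 × sachets used / (calendar days × single rate).

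**Inpatient: c correction days, then m days at 5 g daily.** Sachets used = 6c + m.

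- Example, c = 2 and m = 5: 17 sachets in 7 days. At 6 a day, 17/42 = 40.5%. At 1 a day, 17/7 = 242.9%.
- At 6 a day, the ratio is 1 − 5m/[6(c + m)]. It is largest at c = 3, m = 1: 19/24 = 79.2%.
- At 1 a day, the ratio is 1 + 5c/(c + m). It is smallest at c = 1, m = 20: 26/21 = 123.8%.
- So all 57 combinations (20 + 19 + 18 for c = 1, 2, 3, with m at least 1 and c + m at most 21) fall below 80% at the correction rate and at or above 120% at the maintenance rate.

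**Outpatient: dose change within 180 days.**

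| Change | Sachets used | Starting rate | Last rate |
|---|---|---|---|
| 5 g to 10 g daily, day 30 | 30 + 300 = 330 | 330/180 = 183.3% | 330/360 = 91.7% |
| 5 g to 10 g daily, day 90 | 90 + 180 = 270 | 270/180 = 150.0% | 270/360 = 75.0% |
| 5 g to 10 g daily, day 150 | 150 + 60 = 210 | 210/180 = 116.7% | 210/360 = 58.3% |
| 5 g daily to every other day, day 90 | 90 + 45 = 135 | 135/180 = 75.0% | 135/90 = 150.0% |

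A change at mid-period is out of band under both choices. An early or late change stays in band under one of them.

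**Outpatient: constant dose with one pause.** Compliance = 100 × (span − pause)/span.

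- 14 of 180 days: 166/180 = 92.2%.
- 36 of 180 days: 144/180 = 80.0%, still in band.
- 37 of 180 days: 143/180 = 79.4%, out of band.
- A 14-day pause falls below 80% only when the span is under 14/0.2 = 70 days.

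**With a summed denominator.** Inpatient example: 17/(2 × 6 + 5 × 1) = 100%. Change to 10 g at day 90: 270/(90 × 1 + 90 × 2) = 100%. 14-day pause: 166/(166 × 1 + 14 × 0) = 100%.

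**The case against.** The best defence is that the rate term is undefined after a dose change and is not stated to be fixed. Protocol 6.6 records the dates of delays, reductions and increases, so a programmer could sum prescribed sachets day by day and get about 100% for titrated participants. That is right, and nobody should infer that the SAP orders one fixed rate. But fixing the rule is the SAP's job, and the defence covers only the rate. The day count is explicit and includes paused days, so an instructed pause lowers the score unless someone adds an unwritten zero. Counting such a pause as zero is itself a convention, which is a reason to write it down.

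Other limits on the point also stand:

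- The SAP bands are numeric. A reader might infer that affected participants are declared non-compliant or overdosed, but the SAP attaches no such label.
- Pauses alone rarely matter. Over the full outpatient phase, 14 days leaves the score at 92.2%, and nothing in the documents suggests that pauses beyond 36 days are expected.
- Participants already normokalaemic at baseline can start directly on maintenance, and one inpatient rate may be correct for them.
- These tables are not the only account of dose. SAP 4.6.1.2 also plans g/day, cumulative dose, maximum dose, and prescribed daily dose by visit period.
- A reader might infer from SAP 4.6.1.1 that 5 g every other day would be reported as 5 g/day. That is a strained reading: the denominator is explained as excluding interruptions, and a scheduled off day is not one. Average dose and compliance are also different quantities, so treating pauses differently in the two sections is not a contradiction.

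**Conclusion.** The point holds as a defect in a descriptive derivation. The written product of one rate and a calendar span does not fit a design with changing doses and instructed pauses.

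The effect is largest in the inpatient period: under either prescribed rate, every fully adherent participant with 1 to 3 days of correction followed by 5 g daily scores outside 80 to <120%. For a mid-period outpatient change between 5 g and 10 g daily, the score is 75% or 150% according to a choice the SAP leaves open. Pauses have a small effect unless more than 20% of the span is paused.

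This rests on whole-day dosing, maintenance held at 5 g daily in hospital, and a stay of at most 21 days. The protocol allows longer stays with approval; with 1 correction day, the maintenance-rate score first drops below 120% at 26 days (31/26 = 119.2%).

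It would be wrong to infer any threat to the efficacy results. SAP 3.2 defines the Per Protocol Set by important protocol deviations, the criteria in SAP 3.3.5 do not cite this percentage, and no efficacy analysis uses it. The protocol deviation management plan is not among the documents and could not be checked.

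**What to change.** In SAP 4.1.9.1, replace the denominator with the sum, over the dosing intervals recorded in the eCRF, of days in the interval times sachets prescribed per day in that interval. State that every-other-day dosing counts as 0.5 per day and that investigator-instructed pause days count as 0. Show the multiplication by 100, which the printed formula omits. Full adherence then gives 100%, apart from a half-sachet end effect with every-other-day dosing: 90 doses over a 179-day span give 90/89.5 = 100.6%.

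Optionally, add one sentence to SAP 4.6.1.1 that the scheduled off days of every-other-day dosing are not interruptions.

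The cost is a few lines of SAP text and modest programming. No new data are needed, because Protocol 6.6 already requires the start, stop, delay and dose-change dates.
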